16.6 Monitoring of the trial

This clinical trial will be monitored by the Mayo Clinic Cancer Center Data and Safety Monitoring Board (MCCC DSMB). The study statistician will prepare a report containing accrual and adverse event that will be submitted to MCCC DSMB every 6 months.

16.61 Safety Stopping rules

After every 5th patient has been enrolled, the tolerability of the regimen will be examined. If 2 out of the first 5 patients enrolled or more than 25% of the patients thereafter develop a grade 4 adverse event anything during the course of treatment that is considered possibly, probably, or definitely related to treatment,

enrollment will temporarily close. The study team will review all adverse event data. A trial recommendation will be formulated and presented to the MCCC DSMB – the study may permanently close or may re-open to accrual after MCCC DSMB review and IRB approval of protocol/consent form modifications.

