10.6 Required Routine Reporting

10.61 Baseline and Adverse Events Evaluations

Pretreatment symptoms/conditions to be graded at baseline and adverse events to be graded at each evaluation per CTCAE v4.0 grading **unless** otherwise stated in the table below:

System Organ Class (SOC)	Adverse event/Symptoms	Baseline	Each evaluation
Blood and lymphatic system disorders	Anemia	X	X
	Febrile Neutropenia		X
Cardiac Disorders	Myocardial infarction		X
Gastrointestinal disorders	Nausea	X	X
	Vomiting	X	X
	Abdominal pain	X	X
	Baseline # of stools	X	

	Diarrhea		X
General disorders and administration site conditions	Fatigue	X	X
	Fever		X
Immune system disorders	Allergic reaction		X
	Anaphylaxis		X
Investigations	Neutrophil count decreased		X
	Platelet count decreased		X
	White blood cell decreased		X
	Aspartate aminotransferase increased	X	X
	Alkaline phosphatase increased	X	X
	Blood bilirubin increased	X	X
Musculoskeletal and connective tissue disorders	Arthralgia	X	X
	Myalgia	X	X
Nervous system disorders	Peripheral sensory neuropathy	X	X

10.62 Submit via appropriate MCCC Case Report Forms (i.e., paper or electronic, as applicable) the following AEs experienced by a patient and not specified in Section 10.6:

10.621 Grade 2 AEs deemed *possibly, probably, or definitely* related to the study treatment or procedure.

10.622 Grade 3 and 4 AEs regardless of attribution to the study treatment or procedure.

10.623 Grade 5 AEs (Deaths)

10.6231 Any death within 30 days of the patient's last study treatment or procedure regardless of attribution to the study treatment or procedure.

10.6232 Any death more than 30 days after the patient's last study treatment or procedure that is felt to be at least possibly treatment related must also be submitted as a Grade 5 AE, with a CTCAE type and attribution assigned.

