Neuromuscular & skeletal: Arthralgia, limb pain, myalgia, back pain

Respiratory: Cough, dyspnea, upper respiratory tract infection

Miscellaneous: Fever

Less common known potential toxicities, 1% - 10%:

Dermatologic: Cellulitis

Endocrine & metabolic: Hypothyroidism, hyperthyroidism

Gastrointestinal: Colitis

Infection: Sepsis

Renal: Renal Failure

Respiratory: Pneumonitis, pneumonia

Rare known potential toxicities, <1% (Limited to important or life-threatening):

Adrenocortical insufficiency (immune-mediated), arthritis (immune-mediated), exfoliative dermatitis (immune-mediated), hemolytic anemia (immune-mediated), hepatitis (including autoimmune hepatitis; grade 4: <1%), hypophysitis (grade 2: <1%; grade 4: <1%), interstitial nephritis (with renal failure; grade 3: <1%; grade 4: <1%), Lambert-Eaton syndrome (immune-mediated), myositis (immune-mediated), nephritis (grade 2 autoimmune: <1%), optic neuritis (immune-mediated), pancreatitis (immune-mediated), partial epilepsy (immune-mediated; in a patient with inflammatory foci in brain parenchyma), rhabdomyolysis (immune-mediated), uveitis (immune-mediated)

15.18 **Drug procurement:** Pembrolizumab will be provided free of charge to study participants by Merck.

15.19 **Nursing Guidelines:**

15.191 Pembrolizumab side effects vary greatly from those of traditional chemotherapy and can vary in severity from mild to life threatening.

Instruct patients to report any side effects to the study team immediately. Side effects may be immediate or delayed up to months after discontinuation of therapy. Most side effects are reversible with prompt intervention of corticosteroids.

- 15.192 Diarrhea can be seen however, is less common than that seen with anti-CTLA-4 agents. However it can be severe, leading to colonic perforation. Instruct patients to report ANY increase in the number of stools and/or change in baseline, blood in the stool, abdominal pain to the study team immediately.
- 15.193 Rash/pruritis/dermatitis is seen. Patients should report any rash to the study team. Treat per [Section 9.0](#) and monitor for effectiveness.
- 15.194 Monitor LFT's closely as elevations in these levels could indicate early onset autoimmune hepatitis. Patients should also be instructed to report any jaundice, or right upper quadrant pain to the study team immediately.

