16.0 Statistical Considerations and Methodology

16.1 This pilot study will enroll 10 patients to gain preliminary data on the anti-tumor activity and safety profile of the combination of imiquimod and pembrolizumab in patients with unresectable cutaneous melanoma.

If there are no tumor responses documented among these 10 patients, then upper bound of a one-sided 95% confidence interval for the tumor response rate would be 25.9%.

All patients meeting the eligibility criteria who have signed a consent form and have begun treatment will be evaluable for assessment of all of the clinical endpoints.

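### The safety stopping rule in 16.61 does not count treatment-related deaths, and leaves open when its 25% limb is checked and over which patients

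*Combined protocol and SAP*

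**What the plan says.** Section 16.1 sets the size: "This pilot study will enroll 10 patients to gain preliminary data". Section 16.61 sets the schedule: "After every 5th patient has been enrolled, the tolerability of the regimen will be examined". The trigger is "If 2 out of the first 5 patients enrolled or more than 25% of the patients thereafter develop a grade 4 adverse event", restricted to events "during the course of treatment that is considered possibly, probably, or definitely related to treatment". When it is met, "enrollment will temporarily close. The study team will review all adverse event data". A recommendation then goes to the DSMB, after which the study may close permanently or resume accrual.

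Elsewhere the protocol keeps deaths apart from grade 4. Section 10.62 has one item for grades 3 and 4 (10.622) and another for grade 5, which it equates with death (10.623). Section 10.52 requires a 24-hour expedited report of any death within 30 days of the last dose, and of later deaths at least possibly related to the study agents. Section 16.6 adds a DSMB report every six months, with no numerical threshold.

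On late toxicity, section 15.191 says of pembrolizumab: "Side effects may be immediate or delayed up to months after discontinuation of therapy". Footnote 1 to section 10.41 already requires expedited reports of related serious grade 3, 4 and 5 events more than 30 days after the last administration.

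**The concern.** Safety is half of the primary goal (section 2.1), and section 1.72 says that no study has combined these two agents. Section 16.61 is the only place where a count of events obliges anyone to pause, so its wording has to work without interpretation. It leaves three gaps.

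- **Grade.** The trigger names one grade. Two related deaths among the first five patients, with no separate grade 4 event, would leave it unmet.
- **Timing and denominator.** The 25% limb has no stated checking time other than the fifth-patient schedule, and no stated denominator. Two teams could follow the same paragraph and run different rules.
- **Window.** Events count only during treatment, although the protocol warns of delayed effects and collects related late serious events.

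**Working it through.** **Plan's own figure.** The only computed figure in section 16 is the upper one-sided 95% bound for 0 responses in 10: 1 − 0.05^(1/10) = 0.2589, which reproduces the stated 25.9%. No operating characteristics are given for the stopping rule.

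**Inputs.** N = 10 (16.1). Looks after every fifth enrolment; thresholds of 2 in the first 5, then more than 25% (16.61). I read the first limb as 2 or more. Let p be the true probability that a patient has a counted event, and q = 1 − p. The documents give no rate for related grade 4 events. The nearest figure is the 10-13% expected for serious adverse events (1.9c12), which is only a proxy, so I show p from 10% to 40%. Each outcome is assumed known before the next enrolment.

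**Schedule.** Looks fall at patients 5 and 10. At the second, 10 − 10 = 0 patients remain to be enrolled.

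**Reading A: only the look at 5 can pause accrual.** P = 1 − q⁵ − 5pq⁴. At p = 0.10: 1 − 0.5905 − 0.3281 = 0.0815.

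**Reading B: continuous checking, cumulative denominator.** Since 2/6 = 33%, 2/7 = 29%, 2/8 = 25% (not more than 25%) and 3/8 = 37.5%, the boundary is 2 of 6-7 and 3 of 8-10. The probability of no pause through patient 9 is

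5pq⁴ · q²(1 − p²) + q⁵ · [q² + 2pq(1 − p²)].

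At p = 0.10: 0.3281 × 0.81 × 0.99 + 0.5905 × (0.81 + 0.18 × 0.99) = 0.2631 + 0.5835 = 0.8466, so P(pause) = 0.1534.

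**Reading C: continuous checking, only patients 6 onward in the denominator.** One event in patient 6, 7 or 8 is at least 1/3, so it triggers. A first event in patient 9 is 1/4, which does not. P(pause) = 1 − (1 − P_A) · q³, where P_A is the Reading A probability. At p = 0.10: 1 − 0.9185 × 0.729 = 0.330.

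Chance of an accrual pause before patient 10:

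| True rate | A: look at 5 | B: cumulative | C: patients 6 onward |
|---|---|---|---|
| 10% | 8% | 15% | 33% |
| 20% | 26% | 44% | 62% |
| 30% | 47% | 69% | 82% |
| 40% | 66% | 86% | 93% |

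**First trigger at the scheduled look at 10**, when closing enrolment is moot, for p = 10/20/30/40%: 3.2/12.7/19.7/19.7% with a cumulative denominator (3 or more of 10), or 7.5/19.4/24.9/22.3% counting patients 6-10 only (2 or more of 5).

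**Leaving out deaths.** Take a 10% related grade 4 rate and suppose a further 3%, 5% or 10% of patients die of a related event without a prior grade 4 event. These death rates are assumptions. P(2 or more of 5) is 8.2% for grade 4 alone. Counting both grades, it is 12.9%, 16.5% and 26.3%.

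**The case against.** The strongest reply is that the protocol does not ignore deaths. They are reported within 24 hours, the sponsor must notify the FDA and investigators of serious unexpected suspected reactions (section 10.0), related late serious events are expedited, and the DSMB sees adverse event data every six months. In practice a study team would hardly pass over two related deaths because the rule says grade 4. All of that stands, but none of it is linked to the trigger. Where the protocol means to include grade 5 it says so, as in the reporting timeframes of 10.41. A stopping rule should not depend on inferred intent.

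Three stronger readings are tempting, and the documents do not support them.

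- **The second look can do nothing.** Only the immediate closing of enrolment is moot. Section 16.61 also requires adverse event review and a DSMB recommendation and allows permanent closure. Treatment can last two years (section 7.1), so a late trigger can still matter to patients on drug.
- **The rule acts exactly once, between patients 5 and 6.** That follows from the stated schedule, but the sentence with the thresholds does not confine the second limb to scheduled looks. It can be read as continuous checking from patient 6. The supportable defect is that the text does not decide.
- **The fifth patient will be unexposed at the first look.** Section 16.61 places the look after the fifth enrolment without fixing the moment, and section 6.6 requires treatment to start within 14 days of registration. No minimum follow-up is stated, but that does not show the look would come before exposure.

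**Conclusion.** The grade 5 omission is wrong as written. Followed literally, treatment-related deaths do not count toward the only numerical safety trigger. The timing and denominator of the 25% limb are undefined, and the choice matters: at a 20% true event rate the chance of pausing accrual before patient 10 is 26%, 44% or 62% depending on the reading.

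These figures assume independent patients with a common event rate and each outcome known before the next enrolment; delayed outcomes would lower the chance of a timely pause. The 10-40% range is illustrative. The conclusion about deaths rests on the text alone.

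**What to change.** Amend section 16.61 as follows.

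- Count any grade 4 or 5 adverse event at least possibly related to treatment, including related events reported after the last dose, which 10.41 footnote 1 already collects when serious.
- Keep the sponsor's thresholds, but check them whenever a qualifying event is reported.
- State that the 25% is cumulative over all enrolled patients: after 2 of the first 5, the boundary is 2 of 6-7 and 3 of 8-10.

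The existing path of adverse event review, DSMB recommendation and possible permanent closure can stay as it is, including for a trigger after the tenth enrolment.

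The cost is one paragraph and a somewhat higher chance of a pause, which is reversible. At a 10% counted-event rate it rises from about 8% (look at 5 only) to 15%. It rises further because grade 5 and late events add to the counted rate. If, as an assumption, they took it from 10% to 13%, the Reading B formula gives 1 − (0.2771 + 0.4881) = 23%.

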16.3 Safety Profile

- 16.31 Adverse events will be graded and attribution assigned using CTC CAE version 4.0. For each type of toxicity reported, the proportion of patients experiencing a severe level of that toxicity will be determined.

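### The accrual-stopping rule in Section 16.61 counts related grade 4 events only, so a related death with no separately recorded grade 4 event does not count toward closure

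*Combined protocol and SAP*

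**What the plan says.** Section 16.1 sets the size and purpose: "This pilot study will enroll 10 patients to gain preliminary data on the anti-tumor activity and safety profile". Section 16.3 fixes the scale: "Adverse events will be graded and attribution assigned using CTC CAE version 4.0".

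Section 16.61 holds the only quantitative safety rule.

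- Timing: "After every 5th patient has been enrolled, the tolerability of the regimen will be examined".
- Threshold: "If 2 out of the first 5 patients enrolled or more than 25% of the patients thereafter".
- Counted event: patients who "develop a grade 4 adverse event anything during the course of treatment that is considered possibly, probably, or definitely related to treatment".
- Consequence: "enrollment will temporarily close. The study team will review all adverse event data", followed by a recommendation to the DSMB.

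Elsewhere the protocol separates grade 5 from grade 4. Under routine reporting, item 10.622 covers "Grade 3 and 4 AEs regardless of attribution to the study treatment or procedure", and item 10.623 gives grade 5 its own line, labelled as deaths. Section 10.52 requires expedited reporting within 24 hours of any death within 30 days of the last dose, and of later deaths that are at least possibly related. Section 16.6 sends the DSMB an accrual and adverse event report every 6 months.

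**The concern.** Safety is half of the primary goal in Section 2.1, and Section 1.72 states that the two drugs have not been studied together. The rule in 16.61 is the one place where a safety count leads to a prescribed action on accrual. Followed literally, it ranks a fatal related event below a life-threatening one: the second moves the count and the first need not. A rule of this kind is fixed in advance so that a pause does not depend on judgement at the time. Here the worst outcome is the one left to judgement.

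**Working it through.** **1. Plan's own figures.** The stopping rule has no stated error rate or operating characteristic, so there is nothing to reproduce for it. The only computed figure in Section 16 concerns response: the one-sided 95% upper bound with 0 of 10 responders is 1 − 0.05^(1/10) = 0.2589. This matches the stated 25.9% and is not an input here.

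**2. Does grade 4 include grade 5 in this protocol?** When the authors mean more than one grade, they say so:

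- 10.31 names grades 4 and 5 together.
- 10.41 has a timeframe column for grades 3 to 5, and its footnote lists grades 3, 4 and 5.
- 9.614, 9.622 and 9.653 use an open-ended grade 3 or above.
- 10.622 and 10.623 put grades 3 and 4 on one line and grade 5 on another.

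Against that usage, an unqualified grade 4 in 16.61 does not include death.

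**3. Does another section close the gap?** Sections 10.52 and 10.623 require reporting. Section 16.6 provides periodic DSMB review. None of them prescribes an accrual hold.

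**4. The rule applied to simple cases (no rates needed).** I read 2 of the first 5 as at least 2.

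| First 5 patients | Count as written | Closure as written | Count with grade 5 included | Closure with grade 5 included |
|---|---|---|---|---|
| Two related grade 4 laboratory events | 2 | Yes | 2 | Yes |
| Two related deaths, no recorded grade 4 event | 0 | No | 2 | Yes |
| One related death, no recorded grade 4 event | 0 | No | 1 | No |
| Two deaths, each after a recorded related grade 4 event | 2 | Yes | 2 | Yes |

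The second limb behaves the same way. More than 25% means at least 3 of 10 if counted cumulatively (2/10 = 20%, 3/10 = 30%), or at least 2 of patients 6 to 10 if counted separately (1/5 = 20%, 2/5 = 40%). The text does not say which. On either reading, deaths without a recorded grade 4 event contribute 0.

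**5. Illustrative size at the first look.** The documents give no related grade 4 or grade 5 rate, so these rates are assumptions. Let p4 be the per-patient rate of a related grade 4 event, set at 10%. Let p5 be the rate of a related death with no counted grade 4 event. Patients are independent and the two categories do not overlap. With p the counted rate,

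P(at least 2 of 5) = 1 − (1 − p)^5 − 5p(1 − p)^4.

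| p5 | p if grade 5 counts | Calculation | P(at least 2 of 5) |
|---|---|---|---|
| not counted (as written) | 0.10 | 1 − 0.5905 − 0.3281 | 8.1% |
| 1% | 0.11 | 1 − 0.5584 − 0.3451 | 9.7% |
| 2% | 0.12 | 1 − 0.5277 − 0.3598 | 11.2% |
| 5% | 0.15 | 1 − 0.4437 − 0.3915 | 16.5% |
| 10% | 0.20 | 1 − 0.3277 − 0.4096 | 26.3% |

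**6. Which rows are plausible?** Section 1.9c12 expects about 10% to 13% of patients to have any serious adverse event. Combined rates of 11% to 12% sit inside that range; 15% to 20% sit above it. The comparison is rough, because serious is not the same as grade 4 or 5, as Section 10.1 itself notes.

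**The case against.** The best case against the point has five parts.

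- **Accrual would not necessarily continue.** A reader might infer that the trial would go on enrolling after a related death. The documents do not say that. Deaths reach the sponsor within 24 hours (10.52), serious unexpected suspected reactions go to FDA and all participating investigators (10.0), unanticipated problems go to the IRB (10.51), and a DSMB monitors the trial (16.6). The tolerability examination after every 5th patient is also not confined to the grade 4 count. This stands: only the automatic trigger is missed. But these routes permit a halt and do not require one.
- **Not every related death is missed.** A reader might infer that no related death ever counts. A patient with a recorded related grade 4 event during treatment who later dies is counted through that event. This stands, and the point is limited accordingly.
- **The larger probabilities are not a forecast.** Related death rates of 5% to 10% on top of 10% grade 4 exceed what Section 1.9c12 suggests for all serious events. This stands. At 1% to 2% the change is modest.
- **Practical reach is short.** With 10 patients planned, enrollment is complete by the second scheduled look, so closure then has little left to stop. This stands unless the 25% limb is applied continuously. The first look, with half the patients still to enroll, is where the rule matters.
- **It may be a drafting slip.** The counted-event phrase is visibly garbled, so a deliberate exclusion of deaths should not be inferred. But nothing in the documents supplies the intended wording, and a team following the rule should not have to guess it.

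**Conclusion.** The point holds in limited form. As written, the protocol's only quantitative accrual-stopping rule does not count a related death unless a related grade 4 event was also recorded for that patient, and no other section prescribes a hold. That conclusion rests on the wording and on the protocol's consistent separation of grades 4 and 5, not on any assumed rate.

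The probability effect does depend on assumptions: 10% related grade 4, independent patients, and no overlap between the two event categories. Under these, the chance of closure at the first look rises from 8.1% to between 9.7% and 11.2% at added death rates of 1% to 2%. The 16.5% to 26.3% range needs rates above the protocol's own rough expectation. The documents do not support a claim that deaths would go unnoticed or that enrollment must proceed after one.

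**What to change.** In Section 16.61, change the counted event from grade 4 to grade 4 or 5, keep the attribution wording and both thresholds, and remove the stray word after the event term. Reconcile the section with 10.52 and 10.623, so that a death reported there as at least possibly related to treatment also enters the count.

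This makes a fatal related event count at least as much as a grade 4 event. It does not close enrollment after a single death, which would be 1 of 5 against a threshold of 2. Whether one related death should trigger its own review is a separate decision that the sponsor should state either way.

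The cost is a few words by amendment and a slightly higher chance of a temporary accrual pause. Endpoints, sample size and treatment are unaffected.

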16.7 Inclusion of Women and Minorities

Accrual Targets			
Ethnic Category	Sex/Gender		
	Females	Males	Total
Hispanic or Latino	0	0	0
Not Hispanic or Latino	4	6	10
Ethnic Category: Total of all subjects*			
Racial Category			
American Indian or Alaskan Native			
Asian			
Black or African American			
Native Hawaiian or other Pacific Islander			
White	4	6	10
Racial Category: Total of all subjects*	4	6	10

- Ethnic Categories:** **Hispanic or Latino** – a person of Cuban, Mexican, Puerto Rican, South or Central American, or other Spanish culture or origin, regardless of race. The term “Spanish origin” can also be used in addition to “Hispanic or Latino.”
- Not Hispanic or Latino**
- Racial Categories:** **American Indian or Alaskan Native** – a person having origins in any of the original peoples of North, Central, or South America, and who maintains tribal affiliations or community attachment.
- Asian** – a person having origins in any of the original peoples of the Far East, Southeast Asia, or the Indian subcontinent including, for example, Cambodia, China, India, Japan, Korea, Malaysia, Pakistan, the Philippine Islands, Thailand, and Vietnam. (Note: Individuals from the Philippine Islands have been recorded as Pacific Islanders in previous data collection strategies.)
- Black or African American** – a person having origins in any of the black racial groups of Africa. Terms such as “Haitian” or “Negro” can be used in addition to “Black or African American.”
- Native Hawaiian or other Pacific Islander** – a person having origins in any of the original peoples of Hawaii, Guam, Samoa, or other Pacific Islands.
- White** – a person having origins in any of the original peoples of Europe, the Middle East, or North Africa.

